### 5.2 Secondary objectives and endpoints

*Secondary objective 1:*

- To compare dose regimens of VRC07-523LS delivery for their ability to sustain mucosal mAb levels at serial timepoints post repeat administration

*Secondary endpoint 1:*

- Levels of VRC07-523LS in genital and rectal secretions and tissue at specified timepoints

*Secondary objectives 2:*

- To determine whether ADA can be detected in serum

*Secondary endpoint 2:*

- Serum concentration of ADA in each group measured at multiple timepoints from baseline through the final study visit

### **5.3 Exploratory objectives**

*Exploratory objective 1:*

To assess the acceptability and tolerability of repeat mucosal sampling, including secretions and biopsies, for application in future studies

*Exploratory objective 2:*

To develop predictive mucosal population pharmacokinetic models of VRC07-523LS administered IV

*Exploratory objective 3:*

To conduct analyses related to furthering the understanding of HIV, monoclonal antibodies, immunology, vaccines, and clinical trial conduct

## 6 Statistical considerations

### 6.1 Accrual and sample size calculations

Recruitment will target accruing a total of 24 healthy, HIV-1–uninfected adult participants in two treatment groups, with 12 participants assigned to each group.

In Group 1, all study participants will receive three IV administrations of VRC07-523LS at the 10 mg/kg dose level. In Group 2, all study participants will receive three IV administrations of VRC07-523LS at the 30 mg/kg dose level.

In both groups, the three infusions will be administered every 16 weeks.

Participants will be randomly assigned to either one of the groups. Groups 1 and 2 will open to randomization at the same time.

In Groups 1 and 2, every study participant will be followed for 12 months (including 8 months of product administration plus 4 months of follow-up) from the day of first product administration.

To ensure balance in the trial of both sexes assigned at birth, the trial will enroll at least and approximately 50% of participants assigned female sex at birth. Randomization will be stratified by assigned sex at birth to ensure balance within each treatment group.

The times at which samples will be collected are listed in [Table 9-1](#) and [Table 9-2](#) for each mucosal site and the blood.

Since enrollment is concurrent with the first biopsy sample collection, all participants will provide some data regarding tolerability of mucosal sample collections. For analyses of VRC07-523LS levels in serum and mucosa and of data from ADA assays, it is possible that data may be missing for various reasons, such as participants terminating from the study early, problems in shipping specimens, or high assay background. Immunogenicity data from 17 phase 1 and 2 phase 2a HVTN vaccine trials, which began enrolling after June 2005 (data as of September 2014), indicate that 17% is a reasonable estimate for the rate of missing data. In HVTN 104 (phase 1 trial of VRC01), approximately 10-15% of drug concentration data were missing at the primary timepoints.

#### 6.1.1 Sample size calculations for safety

The goal of the safety evaluation for this study is to identify safety concerns associated with product administration. All participants who receive at least one product administration will be included in this analysis. The ability of the study to detect SAEs can be expressed by the true event rate above which at least 1 SAE would likely be observed and the true event rate below which no events would likely be observed. Specifically, for each treatment group of size  $n = 12$ , there is

at least 90% chance of observing at least 1 event if the true rate of such an event is 17.5% or more; and there is at least 90% chance of observing no events if the true rate is 0.87% or less. For both groups combined (n = 24), there is at least 90% chance of observing at least 1 event if the true rate of such an event is 9.2% or more; and there is at least 90% chance of observing no events if the true rate is 0.43% or less. As a reference, in HVTN vaccine trials from December 2000 through April 2014, about 4% of participants who received placebos experienced an SAE.

Binomial probabilities of observing 0, 1 or more, and 2 or more events among arms of sizes 12 and 24 are presented in [Table 6-1](#) for a range of possible true AE rates. These calculations provide a more complete picture of the sensitivity of this study design to identify potential safety problems with VRC07-523LS.

**Table 6-1 Probability of observing 0 events, 1 or more events, and 2 or more events, among groups of size 12 and 24 for a range of true event rates**

True event rate (%)	arm size	0 events	1+ events	2+ events
1	12	0.89	0.11	0.01
	24	0.79	0.21	0.02
4	12	0.61	0.39	0.08
	24	0.23	0.77	0.42
10	12	0.28	0.72	0.34
	24	<0.02	>0.98	0.89
20	12	0.07	0.93	0.73
	24	<0.01	>0.99	>0.99
30	12	0.01	0.99	0.91
	24	<0.01	>0.99	>0.99

An alternative way of describing the statistical properties of the study design is in terms of the 95% confidence interval (CI) for the true rate of an AE based on the observed data. [Table 6-2](#) shows the 2-sided 95% CIs for the probability of an event based on a particular observed rate. Calculations are done using the score test method (57). If none of the 12 participants in either Group 1 or Group 2 experiences a safety event, the 95% 2-sided upper confidence bound for the true rate of such events in the population is 24.2%. If none of the 24 participants enrolled in Groups 1 and 2 experiences a safety event, the 95% 2-sided upper confidence bound for the true rate of such events in the population is 13.8%.

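### Seven n = 24 entries in Protocol Table 6-1 are wrong and all overstate the chance of seeing safety events; separately, one lower confidence limit in Table 6-2 is about ten times too low

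*Protocol*

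**What the plan says.** The target is 24 participants in two groups of 12: "Recruitment will target accruing a total of 24 healthy, HIV-1–uninfected adult participants in two treatment groups, with 12 participants assigned to each group". Table 6-1 carries the caption "Probability of observing 0 events, 1 or more events, and 2 or more events, among groups of size 12 and 24". Section 6.1.1 describes it as "Binomial probabilities of observing 0, 1 or more, and 2 or more events among arms of sizes 12 and 24" and offers it as a fuller account of how sensitive the design is to safety problems.

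For arm size 24 the table prints, in the order 0 events, 1 or more, 2 or more:

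- 4% true rate: "0.23 0.77 0.42"
- 10% true rate: "<0.02 >0.98 0.89"
- 20% true rate: "<0.01 >0.99 >0.99"

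The prose just before the table says that 24 participants give "at least 90% chance of observing at least 1 event if the true rate of such an event is 9.2% or more". As a reference rate it notes that in past vaccine trials of the network "about 4% of participants who received placebos experienced an SAE".

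Table 6-2 gives two-sided 95% intervals by the score method. For 1 event in 24 it prints limits of 0.07% and 20.2%.

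**The concern.** The prose and the table cannot both describe 24 participants. If the chance of at least one event is about 90% at a true rate of 9.2%, it cannot exceed 98% at 10%.

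Safety and tolerability at each dose are primary objectives, and the trial has no placebo group. Table 6-1 tells an ethics committee or safety board how much reassurance an absence of events, or a small number of them, would carry. If its entries are too favourable, a quiet safety record in 24 people reads as stronger evidence than it is. The 4% row matters most, because 4% is the SAE rate that the protocol itself cites for comparison.

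**Working it through.** **Inputs.** Arm sizes 12 and 24 and true rates of 1, 4, 10, 20 and 30% (Table 6-1); the prose thresholds in section 6.1.1; the score method for Table 6-2.

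**Formulas.** For n participants and true rate p:

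- P(0) = (1 − p)^n
- P(1+) = 1 − P(0)
- P(2+) = 1 − P(0) − n·p·(1 − p)^(n−1)

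**What reproduces.** The prose thresholds are right:

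- n = 12: 1 − 0.825^12 = 0.901 and 0.9913^12 = 0.900
- n = 24: 1 − 0.908^24 = 0.901 and 0.9957^24 = 0.902

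All n = 12 rows of Table 6-1 reproduce. So do the n = 24 rows at 1% (0.786 / 0.214 / 0.024) and at 30% (0.0002 / 0.9998 / 0.998).

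**What does not reproduce (n = 24).**

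- 4%: P(0) = 0.96^24 = 0.375; P(1+) = 0.625; P(2+) = 1 − 0.3754 − 24 × 0.04 × 0.96^23 = 1 − 0.3754 − 0.3754 = 0.249
- 10%: P(0) = 0.90^24 = 0.080; P(1+) = 0.920; P(2+) = 1 − 0.0798 − 24 × 0.10 × 0.90^23 = 1 − 0.0798 − 0.2127 = 0.708
- 20%: P(0) = 0.80^24 = 0.0047; P(1+) = 0.9953; P(2+) = 1 − 0.0047 − 24 × 0.20 × 0.80^23 = 1 − 0.0047 − 0.0283 = 0.967

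| True rate | Quantity | Printed for n = 24 | Exact, n = 24 | Exact, n = 36 |
|---|---|---|---|---|
| 4% | 0 | 0.23 | 0.375 | 0.230 |
| 4% | 1+ | 0.77 | 0.625 | 0.770 |
| 4% | 2+ | 0.42 | 0.249 | 0.425 |
| 10% | 0 | <0.02 | 0.080 | 0.0225 |
| 10% | 1+ | >0.98 | 0.920 | 0.9775 |
| 10% | 2+ | 0.89 | 0.708 | 0.887 |
| 20% | 0 | <0.01 | 0.0047 | 0.0003 |
| 20% | 1+ | >0.99 | 0.9953 | 0.9997 |
| 20% | 2+ | >0.99 | 0.967 | 0.997 |

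Seven cells are wrong for n = 24: all three at 4%, all three at 10%, and the 2+ cell at 20%. The other two cells at 20% hold for n = 24.

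The printed rows lie close to n = 36 (at 4%, P(2+) is 0.42495 before rounding, hence 0.42). The fit is not perfect. At 10%, n = 36 gives 0.0225 and 0.9775, which round to 0.02 and 0.98 but do not satisfy the printed inequality signs. A group of 38 satisfies the signs (0.0182 and 0.9818) but gives 0.90 rather than 0.89 for two or more events.

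**Table 6-2, 1/24.** With p = 1/24 and z = 1.96, the score limits are [p + z²/2n ± z·√(p(1−p)/n + z²/4n²)] / (1 + z²/n).

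- Lower: (0.12170 − 0.11312) / 1.16006 = 0.0074, or 0.74%
- Upper: (0.12170 + 0.11312) / 1.16006 = 0.2024, or 20.2%

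The upper limit and the other five intervals reproduce. The printed lower limit of 0.07% does not. Nor does another common method give it at n = 24: Clopper–Pearson gives 0.105%, the continuity-corrected score interval 0.218%, and Agresti–Coull a value below zero.

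**The case against.** The strongest reply is that little depends on these cells. The target of 24 is not derived from Table 6-1. Comparisons of unsolicited adverse events between arms are descriptive, and safety pauses are triggered by individual events rather than by counts. The main statements of detection ability in the prose are correct, and so are the zero-event upper bounds of 24.2% for 12 participants and 13.8% for 24. The 4% figure is a reference from placebo recipients in earlier vaccine trials, not a rate expected here. All of this stands, and it limits the consequence to how a reader judges the design's sensitivity. It does not make the cells right, and the table is the only place where the protocol gives probabilities at these rates.

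Two cautions on wording also stand. That the rows were computed for n = 36 is inferred from the match; no document says so, and the inequality signs at 10% do not quite fit. The cells are wrong for n = 24 whatever their origin. And the Table 6-2 limit is a separate slip, probably a misplaced decimal. It makes one interval too wide at its lower end and does not affect the chance of seeing events.

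A fault in reading the PDF is not a plausible explanation: the wrong cells agree with one another (0.23 + 0.77 = 1) and follow a consistent pattern.

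**Conclusion.** The concern holds. Seven n = 24 cells of Table 6-1 are arithmetically wrong, all in the favourable direction.

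- At 4%, the chance of at least one event is overstated by about 15 percentage points (77% against 62%) and of at least two by about 17 (42% against 25%).
- At 10%, the overstatements are about 6 points (more than 98% against 92%) and 18 points (89% against 71%). The chance that the whole trial shows no event is 8%, about four times the printed bound of 2%.
- At 20%, the chance of at least two events is overstated by at least 2 points (more than 99% against 97%).

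The Table 6-2 lower limit for 1/24 is 0.74%, about ten times the printed 0.07%.

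The check assumes only what the protocol states: binomial counts in 24 participants, and score intervals. The correction should be made, but it does not alter the sample size, the prose thresholds, the zero-event bounds or any planned analysis.

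**What to change.** In Table 6-1, replace these n = 24 entries (0 / 1+ / 2+):

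- 4%: 0.38 / 0.62 / 0.25
- 10%: 0.08 / 0.92 / 0.71
- 20%: change only the 2+ entry, to 0.97

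In Table 6-2, change the 1/24 interval to [0.7 ; 20.2].

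The prose of section 6.1.1 can stay as it is and will then agree with the table. The cost is eight corrected entries and a less favourable, accurate statement of what 24 participants can show.

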**Table 6-2 Two-sided 95% CIs based on observing a particular rate of safety endpoints for groups of size 12 and 24**

Observed event rate (number of events / sample size)	95% CI (%)
0/12	[0 ; 24.2]
1/12	[1.5 ; 35.4]
2/12	[4.7 ; 44.8]
0/24	[0 ; 13.8]
1/24	[0.07 ; 20.2]
2/24	[2.3 ; 25.8]

**6.1.2 Sample size calculations for serum and mucosal levels**

One of the primary objectives of the study includes assessing the association between the levels of VRC07-523LS measured in serum and in mucosal secretions and tissues at various sites. Measurements will be collected in all 24 participants before the first infusion as well as at several timepoints following the first infusion. The primary statistical analysis will estimate associations between blood and mucosal levels within timepoints. These primary analyses will be conducted irrespective of dose (ie, data from Groups 1 and 2 will be combined) as well as within each treatment group. Additional analyses, secondary in nature, will evaluate association between the levels of VRC07-523LS in serum and in mucosal samples within each birth sex.

The power of the study to detect a significant association between the levels of VRC07-523LS (possibly transformed) measured in serum and in any given mucosa site is shown in [Table 6-3](#) for several values of Pearson’s linear correlation coefficient (r) and sample sizes (n). We anticipate that the primary correlation analysis will be based on samples of sizes n = 12 and n = 24. The secondary correlation analysis will be performed on samples of sizes that are expected to range between n = 5 and n = 15.

In an analysis combining all 24 participants from Groups 1 and 2, the study has more than 72% power to detect a significant association between measurements if the true value of the correlation coefficient is 0.5 or higher. If the true value of the correlation coefficient is 0.6 or higher, the power of the study is greater than or equal to 89.8%.

With 12 participants (eg, in any primary analysis assessing association within a particular treatment group, or in any secondary analysis within a particular birth sex combining both groups), the study has almost 77% power to detect a significant association between measurements if the true value of the correlation coefficient is 0.7 or higher.

With 6 participants (as in any secondary correlation analysis restricted to a specific sex assigned at birth and conducted within a particular treatment group, assuming balance in treatment groups), the study has more than 77% power to

detect a significant association between measurements if the true value of the correlation coefficient is 0.9 or higher.

Additional calculations are reported in the Table that account for 40% to 60% birth sex imbalance within groups. These calculations assumed a two-sided test at the 5% significance level. They were based on Cohen’s method and used an arctanh transformation of the correlation coefficient defined by  $Z' = \text{arctanh}(r) + r/(2(n - 1))$  (58).

**Table 6-3 Statistical power (in percent) to detect a significant association between serum and mucosal VRC07-523LS levels as a function of the sample size (n) for multiple true values of the correlation coefficient (r)**

True correlation coefficient (r)	Sample size (n)						
	5	6	7	9	12	15	24
0.3	8.2	9.1	10.1	12.5	16.0	19.6	30.3
0.4	10.7	12.7	14.8	19.3	26.0	32.6	50.6
0.5	14.5	18.0	21.7	29.2	40.0	49.9	72.6
0.6	19.9	25.7	31.6	42.9	57.6	69.4	89.8
0.7	28.0	36.9	45.4	60.3	76.7	86.9	98.1
0.8	40.5	53.3	64.2	80.0	92.4	97.4	99.9
0.9	62.0	77.2	87.0	96.2	99.4	>99.9	>99.9

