## 9.6 Mucosal sampling

Mucosal secretion and biopsy samples will be collected at the timepoints indicated in [Appendix D](#). All participants in this trial will have consented to mucosal specimen collections. Participants assigned male sex at birth will provide semen, rectal secretions, and rectal biopsies. Participants assigned female sex at birth will provide cervicovaginal and rectal secretions, as well as cervical, vaginal and rectal biopsies. Small (~2-4 mm) tissue biopsies are obtained from the vagina and ectocervix using a speculum and from the rectum by anoscopy by experienced clinicians. The product administration and biopsy collection schedules per mucosal compartment and visit are described in detail in [Table 9-1](#), and also outlined in [Appendix D](#); however, fewer samples may be taken based on the judgment of the performing clinician. The number of biopsies collected per mucosal compartment and visit is shown in [Table 9-2](#). Following the first product administration, a participant may decline all or some of the mucosal biopsies or secretion collections, but they should be encouraged to continue with any collections that they deem acceptable until the end of the trial.

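### The primary serum–mucosa correlation is given n = 24 pooled and n = 12 per arm, but four of the six mucosal specimen types come from one birth sex and supply only about 12 and 6

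*Protocol*

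**What the plan says.** Protocol section 5.1 makes correlating serum and mucosal levels a primary objective. The matching primary endpoint covers genital and rectal secretions and cervical, vaginal and rectal tissue.

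Section 6.1.2 says that all 24 participants contribute measurements, presents Table 6-3 as the power for serum against whichever mucosal site is considered, and makes both the pooled and the within-arm correlations primary. On sample size: "We anticipate that the primary correlation analysis will be based on samples of sizes n = 12 and n = 24".

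One-sex sizes appear only under a secondary label. The n = 12 figure is also said to apply "in any secondary analysis within a particular birth sex combining both groups". The n = 6 figure is introduced "as in any secondary correlation analysis restricted to a specific sex assigned at birth and conducted within a particular treatment group". The intermediate columns of Table 6-3 are explained as follows: "Additional calculations are reported in the Table that account for 40% to 60% birth sex imbalance within groups".

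On who supplies what, section 9.6 says: "Participants assigned male sex at birth will provide semen, rectal secretions, and rectal biopsies". The same section assigns cervicovaginal secretions and cervical and vaginal biopsies to participants assigned female, who also give rectal specimens. Section 6.1 says "the trial will enroll at least and approximately 50% of participants assigned female sex at birth", with randomization stratified by birth sex.

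SAP section 8.3 (Specimens) uses 24 participants for every type: 168 samples for each of three secretion types (504 in all) and 96 for each of three biopsy types (288 in all).

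**The concern.** For semen, cervicovaginal secretions, cervical biopsies and vaginal biopsies, the primary analysis is necessarily a one-sex analysis. No other data exist at those sites. A reader who follows the labels in section 6.1.2 will take the n = 24 and n = 12 columns for the primary result and regard the n = 12 and n = 6 one-sex figures as belonging to a lesser analysis. Nowhere does the plan say that, for four of the six specimen types, the one-sex sizes are the primary ones.

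What is at stake is interpretation. A non-significant serum–genital correlation could be read as evidence against an association when the design had little chance of detecting one. Per-arm sets of about six also lie close to the minimum of five data points that SAP section 8.3 sets for correlations, so some planned primary estimates may never be computed.

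**Working it through.** **Inputs.** Two-sided 5% test and Cohen's method with the stated transformation (section 6.1.2); 24 participants, 12 per arm, about half assigned female (section 6.1); specimen types by sex (section 9.6).

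**Formula.** With t the 97.5% point of the t distribution on n − 2 df:

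- critical r_c = √[t²/(t² + n − 2)]
- Z′ = arctanh(r) + r/(2(n − 1))
- power = Φ[(Z′ − arctanh r_c)√(n − 3)] + Φ[(−Z′ − arctanh r_c)√(n − 3)]

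**Reproducing the plan.** At n = 24, r = 0.5: t = 2.074, r_c = 0.404, arctanh r_c = 0.429, Z′ = 0.560. Then (0.560 − 0.429)√21 ≈ 0.60 and power is 72.6%, as printed. Every cell of Table 6-3 reproduces within 0.1 point.

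**Sizes actually available.** Rectal secretions and biopsies: 24 pooled, 12 per arm. The other four types at a 50:50 split: 24/2 = 12 pooled, 12/2 = 6 per arm.

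**Same formula at those sizes.** At n = 12, r = 0.5: t = 2.228, r_c = 0.576, arctanh r_c = 0.656, Z′ = 0.572. Then (0.572 − 0.656)√9 ≈ −0.25 and power is 40.0%.

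| Primary analysis | True r | Power at stated n | Power at available n (four one-sex types) | Loss (points) |
|---|---|---|---|---|
| Pooled | 0.5 | 72.6% (n = 24) | 40.0% (n = 12) | 32.6 |
| Pooled | 0.6 | 89.8% (n = 24) | 57.6% (n = 12) | 32.2 |
| Per arm | 0.7 | 76.7% (n = 12) | 36.9% (n = 6) | 39.8 |

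The correlation needed for 80% power rises from 0.54 to 0.72 pooled, and from 0.72 to 0.91 per arm.

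**Sex imbalance.** Using the columns the protocol prints for this purpose, pooled power at r = 0.5 runs from 29.2% (n = 9) to 49.9% (n = 15), and per-arm power at r = 0.7 from 28.0% (n = 5) to 45.4% (n = 7). Because the female share is to be at least about half, the three female types lie toward 12–15 pooled and 6–7 per arm, and semen toward 9–12 and 5–6.

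**Missing data.** Section 6.1 gives two rates, which are not applied to the primary n. For an earlier antibody trial, "approximately 10-15% of drug concentration data were missing at the primary timepoints"; for vaccine-trial immunogenicity, past data "indicate that 17% is a reasonable estimate for the rate of missing data". Taking 10–17% and rounding, 24 becomes 22–20, 12 becomes 11–10, and 6 becomes 5.

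| | Pooled, r = 0.5 | Per arm, r = 0.7 |
|---|---|---|
| Rectal types | 68.5–63.8% | 72.0–66.6% |
| One-sex types | 36.5–32.9% | 28.0% |

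If values are missing independently, the chance that six planned points fall below five is 1 − 0.9⁶ − 6(0.1)(0.9⁵) = 0.114 at 10% missing, and 1 − 0.83⁶ − 6(0.17)(0.83⁵) = 0.271 at 17%.

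**SAP specimen counts at 12 women and 12 men.**

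- One per participant-visit: semen 12 × 7 = 84, cervicovaginal 12 × 7 = 84, rectal 24 × 7 = 168, total 336. Biopsies: rectal 24 × 4 = 96, cervical 12 × 4 = 48, vaginal 12 × 4 = 48, total 192.
- Individual specimens (Table 9-2 totals): secretions 12 × 7 + 12 × 14 + 24 × 7 = 420. Biopsies 24 × 8 + 12 × 8 + 12 × 8 = 384.

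Neither unit gives 504 or 288. With 9 to 15 women, secretions are 336 throughout by participant-visit and 399–441 by specimen; biopsies are 168–216 and 336–432.

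**The case against.** The strongest reply is that the plan makes no false statement about any named site. The 72.6% and 89.8% figures are conditional on an analysis combining all 24 participants, and the n = 12 sentence gives its uses only as examples. The smaller columns are printed, power at n = 12 and n = 6 is described in words, and section 6.4.4.1 warns of limited power. Nothing in the design turns on this power: no decision rule uses it, and the primary analysis is framed as estimation with confidence intervals.

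Part of this stands. The correct values are in the table, and the trial's size does not depend on them. But the sentence fixing the primary n makes no exception by site, n = 6 is described only as secondary, and the limited-power remark directly follows the sex-stratified analyses. Reading n = 12 as covering one-sex sites pooled over dose still leaves the per-arm primary n of 6 unstated.

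Three qualifications are fair:

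- The recomputed figures are for an unadjusted Pearson correlation at 5%, as in Table 6-3. SAP section 8.3 also tabulates partial Spearman correlations with false-discovery-rate adjustment, so these are not the power of that test.
- Exactly 40–60% of 24 is 9.6–14.4, so the n = 9 and n = 15 columns lie slightly outside it. Summing 5–7 per arm gives 10–14 pooled and 32.9–46.7% at r = 0.5.
- The 17% rate comes from vaccine immunogenicity data, not drug levels, so the upper end of the missing-data range is the less directly relevant one.

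The SAP specimen counts are a testing tally and change no analysis n; they are a separate, administrative error.

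**Conclusion.** The concern holds. Table 6-3 is right, but the primary sample sizes in section 6.1.2 fit only two of the six specimen types, and those only with no missing data. At the other four, the largest overstatement on the table's grid of r is 32.6 points pooled (r = 0.5) and 39.8 points per arm (r = 0.7). This rests on a near 50:50 sex split and the protocol's own power method. Every imbalance considered leaves power at these sites well below the stated figure. The 11–27% chance of too few points per arm also assumes independent missingness at 10–17%. Participants, samples and conduct are unaffected, but a power stated for a primary objective does not apply at most of the sites, so it should be corrected.

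**What to change.** In protocol section 6.1.2:

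- State n and power for the primary correlation by specimen type: 24 pooled and 12 per arm for rectal secretions and rectal biopsies; about 12 and 6 for semen, cervicovaginal secretions, cervical biopsies and vaginal biopsies, with the imbalance range.
- Say that for these four types the one-sex analysis is the primary analysis.
- Add that a non-significant correlation there is not evidence of no association, and that a per-arm correlation may not be computed if fewer than five points remain.
- Optionally, show the figures after 10–17% missing data.

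In SAP section 8.3, define the counting unit (participant-visit or individual specimen) and recompute the totals by sex. The semen count is wrong on either unit (about 84 at a 50:50 split); the other sex-specific counts depend on the unit chosen.

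The cost is a less favourable stated power at four sites and some redrafting. No further participants or samples are needed.

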- Total IgG truncation: Total IgG (total IgG = Hu IgG1 + Hu IgG2 + Hu IgG3 + Hu IgG4). Any missing subclass will be treated as zero for the purpose of calculating total IgG. If IgG1, IgG2, IgG3, and IgG4 subclasses are all missing for a sample, the sample will be treated as not collected/no sample recovered, and total IgG will be set to NA. Total IgG concentration will be compared to 48 ng/mL; if it is less than 48 ng/mL, the sample will be flagged in the analysis dataset and excluded from the analysis without truncation.
- Total protein truncation: Compared total protein concentration to 0.167 mg/mL, which will be the last curve point and considered as the LLoQ. If concentration < 0.167 mg/mL, then it will be truncated as $0.5 * 0.167$ mg/mL

Body-weight adjustment will be performed by dividing the IgG- and protein-normalized VRC07-523LS levels by the body weight at baseline. Dose-amount adjustment will be performed by dividing the IgG- and protein-normalized VRC07-523LS levels by the body weight at baseline multiplied the dose amount of the products (T1: 10 mg/kg VRC07-523LS, T2: 30 mg/kg VRC07-523LS). The % penetration into different mucosal compartments will be calculated as the protein-normalized VRC07-523LS level in each of the mucosal specimen type divided by that in serum, multiplied by 100.

Pre-treatment participants and all secretion samples deemed hemoglobin-contaminated or unreliable (1. Total IgG concentration < 48 ng/mL, or 2. Total protein concentration < 0.167 mg/mL, with total IgG concentration also < 48 ng/mL) are excluded from the analysis.

Statistical methods

Tabular summaries of the distributions of body-weight-adjusted, IgG- and protein-normalized VRC07-523LS levels, and % penetration of protein-normalized VRC07-523LS is presented by specimen type, treatment arm, sex at birth and visit. Body weight comparisons between treatment arms (T1 vs. T2) and between sexes at birth (Female vs. Male) are presented using the Wilcoxon Rank Sum Test. A table of partial Spearman's rank correlation coefficients of specimen comparison and p-values, adjusted for treatment group (T1 vs. T2) and sex at birth (males vs. females), is presented by visit. P-values are adjusted for multiple comparisons by controlling the false discovery rate (FDR) using the Benjamini-Hochberg procedure [9] and the q-value [10]. Results are significant if the adjusted p-value or q-value ≤ 0.05 .

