The distributions of body-weight-adjusted IgG- and protein-normalized VRC07-523LS levels, and total IgG over time are displayed graphically by specimen type, assigned sex at birth, and treatment arm. Data points for each participant are connected by a gray solid line. Additionally, the distributions of body-weight-adjusted IgG- and protein-normalized VRC07-523LS levels over time are displayed graphically by treatment arm, with all specimen types plotted together. Data points for each participant are connected by a gray dashed line, while median levels at each timepoint for each specimen type are connected by a colored solid line. The distributions of body-weight-adjusted IgG-normalized VRC07-523LS levels over actual study days since enrollment are displayed graphically by specimen type, assigned sex at birth, and treatment arm. Data points for each participant are connected by the colored dashed line.

Correlations of dose-amount-adjusted, IgG-normalized VRC07-523LS concentrations across specimen types by visits are reported in two ways: (1) sex at birth plotted together but distinguished by shapes, and treatment arms plotted together but distinguished by colors (2) separately for female and male participants, and treatment arms plotted together but distinguished by colors. Correlations of IgG-normalized VRC07-523LS concentrations across specimen types by visits are reported in two ways: (1) separately for treatment arms, and sex at birth plotted together but distinguished by shapes (2) separately for treatment arms, and sex at birth. Correlation of IgG levels and protein levels across specimen types by treatment arms and visits are reported as well. Spearman's rank correlation coefficients and their associated p-values are calculated. Comparisons only done when there are at least 5 data points in each group.

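### The stated power for the serum–mucosa correlation is for an unadjusted Pearson test on complete data; allowing for the protocol's own missing data and the SAP's rank tests, pooled power at r = 0.5 is below the 72.6% shown

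*Protocol*

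**What the plan says.** Correlating serum and mucosal levels is part of primary objective 2 (Protocol 5.1). Protocol 6.1.2 gives power for Pearson's linear coefficient. Its headline figure, for the two groups pooled, is that "the study has more than 72% power to detect a significant association between measurements if the true value of the correlation coefficient is 0.5". On sample size it says: "We anticipate that the primary correlation analysis will be based on samples of sizes n = 12 and n = 24". On method, the calculations "used an arctanh transformation of the correlation coefficient defined by" arctanh(r) + r/(2(n − 1)), and "These calculations assumed a two-sided test at the 5% significance level". No covariate and no allowance for missing data enters. The smaller sample sizes in Table 6-3 serve the by-sex analyses and birth-sex imbalance.

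Protocol 6.1, discussing serum, mucosal and ADA data, says that earlier vaccine trials "indicate that 17% is a reasonable estimate for the rate of missing data". It adds that about 10–15% of drug concentrations were missing in HVTN 104.

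Protocol 6.4.4.1 mentions Spearman and Pearson as example measures, with 95% confidence intervals, and leaves detail to the SAP. SAP 8.3 has a table of partial Spearman coefficients which, "adjusted for treatment group (T1 vs. T2) and sex at birth (males vs. females), is presented by visit". For the scatterplots, Spearman's "rank correlation coefficients and their associated p-values are calculated". Pearson does not appear in the SAP. SAP 7 names SAS and R but does not say whether Spearman p-values are exact or approximate.

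**The concern.** The power statements justify the sample size for a primary objective, so they should describe the test that will be run on the data that are expected. They differ from the plan in two ways. The protocol predicts missing data in 6.1 and then powers on full enrolment in 6.1.2. The test is also a Pearson test in the power section and a rank test in the SAP, which under normality is less powerful, most visibly at small n. A reader who takes the stated power at face value would give a non-significant correlation more weight than the test can support.

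**Working it through.** **Inputs.** Two-sided 5% level, the formula and the sample sizes are from Protocol 6.1.2; missingness of 10–17% is from 6.1; the tests are from SAP 8.3.

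**Step 1: reproduce the plan's figure.** The critical correlation is r_c = t/√(t² + n − 2), with t the 97.5% point on n − 2 degrees of freedom. Power is Φ{[arctanh(r) + r/(2(n − 1)) − arctanh(r_c)] × √(n − 3)}, plus a negligible opposite tail.

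For n = 24, r = 0.5: r_c = 0.4044, so arctanh(r_c) = 0.4289. The effect is 0.5493 + 0.5/46 = 0.5602. Then (0.5602 − 0.4289) × √21 = 0.602 and Φ = 72.6%, as stated. The same formula matches every cell of Table 6-3 within 0.1 point.

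**Step 2: keep Pearson and apply only the protocol's missingness.** 24 × 0.90 = 21.6 and 24 × 0.83 = 19.9, so n is about 22 to 20. 12 × 0.90 = 10.8 and 12 × 0.83 = 10.0, so n is about 11 to 10.

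| Case | Complete data (stated) | 10% missing | 17% missing |
|---|---|---|---|
| Pooled, r = 0.5 | 72.6% (n = 24) | 68.5% (n = 22) | 63.8% (n = 20) |
| n = 12, r = 0.7 | 76.7% (n = 12) | 72.0% (n = 11) | 66.6% (n = 10) |

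For n = 20, r = 0.5: r_c = 0.4438, arctanh(r_c) = 0.4769, effect 0.5493 + 0.5/38 = 0.5625, and (0.5625 − 0.4769) × √17 = 0.353, giving 63.8%.

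**Step 3: use the SAP's tests.** Simulation under bivariate normality with r = 0.5. Partial Spearman regresses the ranks on arm and sex and uses n − 4 degrees of freedom. No arm shift is added, so the same r applies to each coefficient.

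| Test, r = 0.5 | n = 24 | n = 22 | n = 20 |
|---|---|---|---|
| Pearson (Table 6-3 formula) | 72.6% | 68.5% | 63.8% |
| Spearman | 66% | 62% | 57% |
| Partial Spearman (arm, sex) | 62% | 57–58% | 52–53% |

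Simulated type I error for the two rank tests is 4.9–5.1% at these sizes.

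**Step 4: the secondary n = 6 analysis, r = 0.9.** Stated power is 77.2%. On complete data, Spearman with an exact p-value needs |ρ| of at least 0.886 and has about 51% power. With the t-approximation (critical value 0.811) power is about 66%, but the true type I error is 5.8%. The SAP does not say which applies.

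**The case against.** **The table is not miscalculated.** This is right. Section 6.1.2 states its coefficient, formula and n openly, and the figures follow from them. A reader might infer an arithmetic error; the documents show only that the figures belong to a different test and to complete data.

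**Protocol 6.4.4.1 still mentions Pearson, and 6.1.2 speaks of estimating associations, with confidence intervals planned.** Both are true. But Pearson is given there as an example and is absent from the SAP, and 6.1.2 goes on to justify n by power for a significant result. Step 2 also shows that the stated power is not met with Pearson itself once the expected data loss is applied.

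**The protocol concedes limited power.** It does so in 6.4.4.1, directly after the sex-stratified analyses. That softens the n = 6 issue but leaves the stated figures uncorrected.

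**The SAP does not say clearly which analysis is the serum–mucosa test.** The scatterplot entries that name specimens name mucosal ones only, while other text says specimen types. This adds to the need for clarity and does not restore 72.6%.

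**Stronger readings that the documents do not support:**
- *True power is simply about 51%.* One could reach that figure by setting the within-arm r at 0.5 and adding a dose shift of ln 3 with assumed log SDs of 0.5 (serum) and 0.8 (mucosa). Those inputs imply a pooled Pearson r of (0.5 × 0.5 × 0.8 + (ln 3)²/4) / √[(0.25 + 0.302)(0.64 + 0.302)] ≈ 0.70. That is a different truth from the pooled 0.5 behind 72.6%.
- *The n = 6 power is 51%.* That holds only with exact p-values, which the SAP does not specify. It owes nothing to missing data, and the analysis is secondary.
- *A known further loss from false-discovery control.* SAP 8.3 applies such control to the partial Spearman table, but neither document defines the family of tests, so no figure can be given.
- *A null result will be read as proof of no link.* Nothing in the documents says so.

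**Conclusion.** Wrong as written: the stated power does not match the planned test or the expected data. Under the protocol's own formula and missingness, pooled power at r = 0.5 is about 64–69% rather than more than 72%, and the n = 12, r = 0.7 figure is about 67–72% rather than almost 77%. Under the SAP's tests with 10–17% missing, pooled power is about 57–62% (Spearman) or 52–58% (partial Spearman).

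The rank-test figures assume bivariate normality and the same r for the Pearson, Spearman and partial correlations. If pooling two doses makes the unadjusted correlation larger than the within-arm one, the unadjusted and adjusted figures separate. The 10–17% is taken as the loss of serum–mucosa pairs. The pooled n applies only to rectal specimens, because semen and cervicovaginal specimens each come from one sex (Protocol 9.6).

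**What to change.** Restate Table 6-3 and the power sentences in Protocol 6.1.2 for the test the SAP will run, Spearman or partial Spearman with its covariates, at n reduced by 10–17%. Alternatively, name Pearson or partial Pearson on log-transformed levels in SAP 8.3, keep Spearman as support, and correct the table for missing data and any covariates. In either case, identify the serum–mucosa test in the SAP and say whether small-sample Spearman p-values are exact or approximate.

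The cost is wording and a recalculated table. The stated figures will look less favourable. No additional participants, visits or samples are needed.
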